1 FLOW CHARTS

1.1 STUDY FLOWCHART

Evaluation ^a	Screening/ Baseline	Cycle 1 ^b				Subsequent Cycles ^b		End of Treatment (EOT)	Post treatment Follow-up Period ^{jj}			
	D-21 to D1	D1	D8	D15	D22	D1	D15	30 days after last IMP admin	At 60 days after last IMP admin	At 90 days after last IMP admin	Beyond 90 days after last IMP admin	
Informed Consent / Inclusion/Exclusion Criteria	X											
Randomization		X										
Demography, Medical/Surgical and Disease History ^c	X											
Physical Examination ^d	X (within 7 days prior to first dose)	X	X	X	X	X	X	X	X	X		
Weight / Height(at baseline only) ^e	X	X	X	X	X	X	X	X				
Vital Signs ^f	X	X	X	X	X	X	X	X	X	X		
Performance Status (ECOG)	X	X	X	X	X	X	X	X				
12-Lead ECG ^g	X											
Chest X-ray ^h	X											
Laboratory Assessments:												
Pregnancy Test ⁱ	X (within 7 days prior to first dose)					X		X	X	X	X	
Hepatitis B virus (HBV) serology		X ^{kk}										
Blood Chemistry ^l	X	X ^l	X	X	X	X	X	X	X	X		
Hematology ^k	X	X ^l	X	X	X	X	X	X	X	X		
Coagulation ^m	X	As clinically indicated										
Urinalysis ⁿ	X	X ^l		X		X	X	X	X	X		
Isatuximab/cemiplimab IAR Labs ^o		Prior C1D1 then if IAR ≥G2										
Markers of potential TLS ^p		As clinically indicated										
Serum β2-microglobulin ^q	X					X		X				
Immunoglobulins: IgG, IgA, IgD, IgE, IgM ^q	X					X		X	X	X		

Evaluation ^a	Screening/ Baseline	Cycle 1 ^b				Subsequent Cycles ^b		End of Treatment (EOT)	Post treatment Follow-up Period ^{jj}		
	D-21 to D1	D1	D8	D15	D22	D1	D15	30 days after last IMP admin	At 60 days after last IMP admin	At 90 days after last IMP admin	Beyond 90 days after last IMP admin
Blood typing interference test ^r	X					C2 only					
PK ^s	See PK/PD Flow-Chart										
ADA ^t	See PK/PD Flow-Chart										
Adaptive immune response (including TCR repertoire) (blood and bone marrow aspirate) ^u	X					C3 (blood only) and in case of CR					
Adaptive immune response (humoral and cellular response) (Blood) ^v		X				C2, C4,C7,C10		X			
Immunophenotyping (Blood and bone marrow aspirate) ^w	X					C3		X (Blood only)			
FISH (bone marrow aspirate) ^x	X										
PD1-PDL1 expression (Bone marrow biopsy) ^y	X					C3		X			
MRD assessment (bone marrow aspirate)	X	In case of CR									
Disease Assessment^z											
- Serum M-Protein ^{aa}	X	X ^l				X		X	X ^{dd}		
- sFLC ^{bb}	X	X ^l				X		X	X ^{dd}		
- Urine M-Protein (24-hr urine) ^{cc}	X	X ^l				X		X	X ^{dd}		
- Bone Marrow for disease assessment ^{ee}	X	to confirm CR and as clinically indicated						X (if clinically indicated)	X (if clinically indicated) ^{dd}		
- Bone disease assessment (Skeletal survey or low-dose whole body CT) ^{ff}	X					X (if clinically indicated)		X (if clinically indicated)	X (if clinically indicated) ^{dd}		
- Plasmacytoma assessment (PET/CT/MRI) ^{gg}	X					X (if clinically indicated)		X (if clinically indicated)	X (if clinically indicated) ^{dd}		
Isatuximab Administration ^{hh}		X	X	X	X	X	X				

Evaluation ^a	Screening/ Baseline	Cycle 1 ^b				Subsequent Cycles ^b		End of Treatment (EOT)	Post treatment Follow-up Period ⁱⁱ		
	D-21 to D1	D1	D8	D15	D22	D1	D15	30 days after last IMP admin	At 60 days after last IMP admin	At 90 days after last IMP admin	Beyond 90 days after last IMP admin
Cemiplimab Administration		X		X		X	X				
AE/SAE Assessment ⁱⁱ	X	Continuously throughout study period						X (ongoing related AE, ongoing SAE, new related AE/SAEs)			
Prior/Concomitant Medication	X (within 21 days prior to first dose)	Continuously throughout study period						X (related to AE/SAEs)			
- New anticancer therapy								X	X		

- a **Evaluation:** Assessments to be performed prior to study treatment and prior to premedication administration unless otherwise indicated. Informed consent should be signed before any study specific procedures. In Phase 2 part, **randomization** to take place once the consented patient has completed all the necessary screening procedures and is deemed eligible for study entry by the Investigator or designee. All eligible patients must be randomized using Interactive Response Technology (IRT). Every effort should be made to start treatment within 3 working days of randomization.
- b **Cycle:** A cycle is 28 days. The treatment window is ± 1 day for each of the weekly administrations ± 2 day for each of the Q2W administrations and ± 4 day for each of the Q4W administrations. A dose is deemed to have been delayed if the treatment is ≥ 2 days beyond the theoretical day of treatment for weekly dose, ≥ 3 days beyond the theoretical day of treatment for Q2W dose and ≥ 5 days beyond the theoretical day of treatment for Q4W dose. The reason for dose delay will be captured. Cycle 1 Day 1 refers to the day the patient receives the first study treatment administration.
- c **Demography:** Includes age, gender and race. **Medical/Surgical History:** Includes relevant history of previous/associated pathologies, other than multiple myeloma including respiratory function history, and smoking status. **Disease History:** Includes date of initial diagnosis, subtype, stage and previous anti-MM therapy (type, duration, reason for discontinuation and response to). In addition, results of additional procedures (such as karyotype, FISH, etc) performed as part of standard of care to assess the current disease status may also be collected. If not previously performed, blood type, phenotype or genotype and screen should be done prior to first study treatment administration. The transfusion service should be made aware that the patient is receiving an anti-CD38 treatment (isatuximab). During the study treatment period the transfusion service should follow the recommendations issued in the AABB bulletin in case a blood red cells transfusion is needed. The web link to the AABB bulletin will be indicated on the study patient card (see [Appendix I](#)). Patients should keep together their study patient card with their blood type card throughout the duration of the study treatment.
- d **Physical Examination:** To be performed at screening (< 7 days prior to first dose), prior to study treatment administration on Day 1, Day 8, Day 15 and Day 22 of Cycle 1, Day 1 and Day 15 of each subsequent cycle, at the EOT visit and post treatment follow up visits at 60 and 90 days after last treatment. Consists of examination of major body systems, including neurological, digestive exam, respiratory (signs and symptoms, respiratory rate), hepatic and spleen span, lymph node examination. Only main diagnoses will be reported in the eCRF as AEs or medical history. Signs and symptoms related to multiple myeloma ongoing at baseline will be recorded in medical history and will be reported in AE page in case they worsen or become serious during study treatment. Laboratory abnormalities at baseline will be recorded in laboratory pages.
- e **Weight / Height:** Height is required at baseline only. Weight is required at Screening, prior to starting infusion and at the EOT visit.
- f **Vital Signs:** Blood pressure, heart rate, temperature, and respiration rate required at Screening, to be taken just before starting infusion, every hour during the infusion, and at the end of infusion on D1, D8, D15 and D22 of Cycle 1; and to be taken just before starting infusion at D1 and D15 of each subsequent cycle and as clinically indicated, at the EOT visit, and at post treatment follow up visits at 60 and 90 days after last treatment.
- g **12-Lead ECG:** To be performed at Screening and then as clinically indicated.
- h **Chest X-ray:** To be performed at Screening and then as clinically indicated.
- i **Pregnancy Test:** Women of child bearing potential must have a negative serum pregnancy test result within 7 days prior to first IMP administration. During the study, test to be done on Day 1 of each cycle prior to the study treatment, at the end of treatment, and then every month for 5 months following the last dose of Isatuximab or 6 months following the last dose of cemiplimab, whichever comes last (urine pregnancy test can be performed at home after study treatment discontinuation).

- j* **Blood Chemistry:** To be done at Screening, then prior to pre-medication and IMP administration on D1, D8, D15 and D22 of Cycle 1 and on D1 and D15 of every subsequent cycle, at the EOT visit, 60 and 90 days after last treatment and as clinically indicated. Blood chemistry includes: SGOT (AST), SGPT (ALT), bilirubin (total and direct), alkaline phosphatase, lactate dehydrogenase (LDH), sodium, potassium, chloride, bicarbonate/carbon dioxide, calcium, corrected serum calcium, magnesium, phosphate, uric acid, urea or blood urea nitrogen (BUN), serum creatinine, eGFR(MDRD formula), glucose (fasting), albumin and total protein. Thyroid stimulating hormone (TSH) will be assessed every second cycle, and free T4 if TSH is outside of the normal range.
- k* **Hematology:** To be done at Screening, then prior to pre-medication and IMP administration on D1, D8, D15 and D22 of Cycle 1 and D1 and D15 of every subsequent cycle, at the EOT visit, 60 and 90 days after last treatment and as clinically indicated. Hematology includes: Hemoglobin, hematocrit, RBC, WBC with differential, and platelet counts. If Grade 4 neutropenia, assess ANC every 2-3 days until $ANC \geq 0.5 \times 10^9/L$ and at least weekly thereafter until $ANC \geq 1.0 \times 10^9/L$. Blood group card to be obtained before study entry.
- l* **Blood chemistry, hematology, urinalysis and efficacy labs** assessments are not required to be repeated prior to D1 Cycle 1 if the screening labs were performed within 3 days prior to first IMP administration.
- m* **Coagulation:** To be done at Screening and then as clinically indicated. Coagulation includes: Prothombin time (PT) or international normalized ration (INR) and activated partial thromboplastin time (PTT).
- n* **Urinalysis:** Quantitative urinalysis (includes Na, K, Ca, Cl, RBC, protein, glucose, pH, ketones, bilirubin, leucocytes, nitrates and specific gravity) to be done at baseline, EOT, 60 and 90 days after last treatment and during the treatment period if hematuria is observed or clinically indicated – Dipstick (qualitative) will be performed on D1 and D15 of each new cycle.
- o* **Isatuximab/Cemiplimab IAR Labs: include cytokines** (TNF- α , IL-1- β , , IL-6, and IFN- γ), markers of complement activation (C3a, C4, CH50) and serum tryptase, lactate dehydrogenase [LDH]. Baseline sample to be drawn prior to first isatuximab administration at Cycle 1. Then if an isatuximab infusion associated reaction (IAR) of \geq Grade 2 occurs, additional blood sampling during the AE is required for analysis.
- p* **Markers of potential TLS:** to be done in case of suspicion of TLS (uric acid, BUN/creatinine, potassium, phosphate, calcium and corrected calcium).
- q* **Serum β 2-microglobulin and Immunoglobulins (IgG, IgA, IgM, IgD and IgE):** To be performed at Screening, D1 of each cycle starting from Cycle 2, and at the EOT visit. After EOT, during the follow up visits, Immunoglobulins to be performed only in patients discontinued study without disease progression and have not started new anti-cancer treatment (IgD or E only if the heavy chain component of the disease is known to be E or D).
- r* **Blood typing interference test:** at screening: blood type (if not already done) and phenotype (according to the site protocol). Recommended phenotype include Rh system (C/c and E/e), Kell system (K/k); Duffy system (Fya/Fyb); Kidd system (Jka/Jkb); MNS system (M/N, S/s), and Indirect Antiglobuline Test (IAT, indirect Coombs test). On Cycle 2 Day 1 and before each transfusion: Indirect Antiglobuline Test (IAT, indirect Coombs test or Antibody screen). Blood type card will be kept by the patient with the study card. Blood transfusions are to be recorded in the eCRF. The blood bank needs to be informed that the patient is receiving a treatment with an anti-CD38 and a potential interference with the Coombs test is possible.
- s* **Pharmacokinetics (PK):** isatuximab and cemiplimab. See PK/PD flow chart.
- t* **ADA (Anti-Drug Antibodies):** isatuximab and cemiplimab. See PK/PD flow chart.
- u* **Adaptive immune response (including TCR repertoire assessment) (Blood and bone marrow):** To be performed at screening, and D1 of Cycle 3 prior to IP administration (blood only) and in case of CR.
- v* Adaptive immune response (humoral and cellular response) (Blood) : To be performed prior to pre-medication and IMP administration on D1 of Cycle 1, Cycle 2, Cycle 4, Cycle 7 and Cycle 10 and in disease progression patients at EOT. Humoral response will be assessed in allsites. Cellular response will be assessed in patients at selected sites.
- w* **Immunophenotyping (Bone marrow aspirate and blood):** To be performed at screening, D1 of Cycle 3 prior to IP administration and at the EOT visit (blood only).
- x* **FISH: Bone marrow aspirate:** to be performed at screening.
- y* **PD1-PDL1 expression (Bone marrow biopsy):** Access to archival bone marrow biopsy material will be requested at screening and if available, retrospective expression analysis will be performed by IHC. For any patients that have bone marrow biopsy available at baseline, there will be optional biopsies performed at pre-dose on Day 1 of Cycle 3 and at the EOT visit.
- z* **Disease Assessment:** All lab tests include M-protein quantification (serum and 24-hour urine, immunoelectrophoresis, and immunofixation) and serum free light chain levels should be repeated on C1D1 if not performed within 3 days prior to first IMP administration, and all radiologic assessments to be performed within 21 days prior to first IMP administration. Response is assessed on the basis of clinical and laboratory findings on D1 of every cycle (starting C2, prior to IMP administration), whenever disease progression is suspected (eg, symptomatic deterioration) and at the EOT visit. The availability of the results must not prevent the initiation of the next cycle.
- aa* **Serum M-Protein:** To be performed at Screening, D1 of every cycle prior to IMP administration (not required to be repeated at Cycle 1 if screening labs were performed within 3 days prior to first IMP administration), and at the EOT visit. Immunofixation to be performed at baseline and required after treatment due to disappearance of the M component in the electrophoresis. An additional serum sample will be collected at all time-points to evaluate the potential interference of isatuximab in the M protein assessment (central laboratory).
- bb* **sFLC:** To be performed at Screening, D1 of every cycle prior to IMP administration (not required to be repeated at Cycle 1 if screening labs were performed within 3 days prior to first IMP administration), and at the EOT visit.

- cc* **Urine M-Protein (24-hr urine):** 24-hour urine collection for Bence Jones protein with urine electrophoresis at Screening, D1 of every cycle prior to IMP administration (not required to be repeated at Cycle 1 if screening labs were performed within 3 days prior to first IMP administration), and at the EOT visit. Urine immunofixation to be performed in this 24 hours urine at baseline and if required due to disappearance of the M component in the electrophoresis. If negative at baseline, to be repeated every 3 months and to confirm response or PD.
- dd* **Disease assessments during follow-up period** are only required for patients have discontinued study treatment for reasons other than disease progression and have not yet started treatment with another anti-cancer therapy. Patients will be followed every month for progression during this period. Disease assessments required every month include evaluation of serum M-protein, serum free light chains and urine M-protein. A bone marrow, skeletal survey and PET/CT/MRI are only required if clinically indicated to confirm response or progression according to IMWG criteria. Disease assessments not required once patient starts treatment with another anti-cancer therapy.
- ee* **Bone marrow (biopsy/aspiration) for disease assessment:** To be performed at Screening, to confirm a sCR, CR and as clinically indicated.
- ff* **Bone disease assessment:** Skeletal survey (including skull, spine, all long bones, pelvis and chest) or low-dose whole body CT scan at baseline (within 21 days prior to study treatment), and during the trial as clinically indicated and to confirm response according to IMWG criteria.
- gg* **Plasmacytoma assessment (including extramedullary and bone plasmacytoma):** PET/CT/MRI scan too be performed at screening in patients with known or suspected extramedullary disease, and during the trial as clinically indicated and to confirm response according to IMWG criteria. The same modality (PET-CT or MRI) should be used throughout the study for each individual patient.
- hh* **Cemiplimab/Isatuximab Administration:** At the start of each treatment cycle, the patient's weight will be determined.
- ii* **AE/SAE assessment:** All AEs, including adverse events of new onset as well as worsening of baseline signs and symptoms are to be reported from the signing of the informed consent to 30 days following the last administration of study treatment. After the 30 day all ongoing **related non-serious AEs, ongoing SAE** and **new related AE/SAEs** are to be followed to resolution or stabilization. Severity will be graded according to NCI-CTC v4.03.
- jj* **Follow-up:** The post-treatment follow-up period includes an extended safety follow-up period of 90 days after the last dose of study treatment, and further follow up beyond the 90 days after the last dose of study treatments until death or final study cut-off date, whichever occurs first.
Patients who discontinue study treatment due to PD: follow-up visit will be done every 3 months from the date of last study treatment administration until death or final study cut-off date. Every effort will be made to follow all patients. If survival follow-up is missed and is not obtained at the time of the scheduled interval, it should be retrieved immediately. For subsequent survival follow-up, the patient FU visit should be scheduled at the original scheduled survival follow-up interval. If the patient is unable to visit the clinical center, the follow-up may be done via phone from the Investigator or designee to the patient or the patient's caregiver or a family member, but this should be exception and any effort should be done to schedule follow-up visit at clinical center.
Patients who discontinue the study treatment without PD: will be followed every month for disease assessment until confirmation of PD or start treatment with another anti-cancer therapy whichever comes first. After PD patient will be followed every 3 months as described just above.
- kk* Includes HBsAg, anti-HBsAb, and anti-HBcAb (total and IgM) and HBV DNA in case of positive anti-HBsAg (see [Section 6.5.7](#)). Once at any time if HBV status unknown before treatment started and to be repeated if clinically indicated for patient still on treatment at the time of amended protocol 05.

Abbreviations: ADA=anti-drug antibodies; AE=adverse event; ALT=alanine aminotransferase; ANC=absolute neutrophil count; ALP=alkaline phosphatase; AST=aspartate aminotransferase; BUN=blood urea nitrogen; C=Cycle; CR=complete remission; CRF=case report form; D=Day; ECG=electrocardiogram; ECOG=Eastern Cooperative Oncology Group; EOT=end-of-treatment visit; FUP=follow-up visit; HBcAb=hepatitis B core antibody; HBsAb=hepatitis B surface antibody; HBsAg=hepatitis B surface antigen; HBV=hepatitis B virus; IgM=immunoglobulin M; IMP=investigational medicinal product; INR=international normalized ratio; LDH=lactate dehydrogenase; MDRD=Modification of Diet in Renal Disease Study; PD=pharmacodynamic or progressive disease; PK=pharmacokinetic; PR=partial remission; PS=performance status; PT=prothrombin time; aPTT=activated partial thromboplastin time; SAE=serious adverse event; sFLC=serum free light chain, SGOT=serum glutamate-oxalate transferase; SGPT=serum glutamate-pyruvate transferase; WBC=white blood cell.

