1.2.2 Isatuximab QW/Q2W + cemiplimab Q2W (DL1) - Treatment phase: Cycle 2 and beyond (Sparse sampling)

Procedure		Treatment Phase											
		C2~C3					C4					C5 and beyond ^d	
		D1		D15			D1		D15			D1	
Cemiplimab	IV infusion	X-----X			X-----X			X-----X			X-----X		X---
	Sample RNT (h)	SOI	EOI		SOI	EOI	SOI	EOI			SOI	EOI	SOI
	Sample Time window	[-24h,SOI]	[-5 min,EOI]		[-24h,SOI]	[-5 min,EOI]	[-24h,SOI]	[-5 min,EOI]			[-24h,SOI]	[-5 min,EOI]	[-24h,SOI]
	PK sample ID	S00	S01		S02	S03	S00	S01			S02	S03	S00
	ADA Sample ID ^a	AB00 (C2)											AB00 ^a
Procedure		C2~C3					C4					C5 and beyond ^d	
		D1		D15			D1		D15			D1	
			X-----X			X---			X-----X			X---	
Isatuximab	IV infusion	SOI		EOI	SOI		SOI		EOI	EOI+1h	SOI		SOI
	Sample RNT (h)			±10min					±10min	±10min			
	Sample Time window												
	PK sample ID ^b	P00 ^c		P01 (C2)	P02 ^c		P00 ^c		P01	P02	P03 ^c		P00 ^c
	ADA Sample ID ^b	AB00 ^c					AB00 ^c						AB00 ^c

- ^a For cemiplimab ADA during treatment phase, samples to be collected every third Cycle from C5 (ie, on D1 of C5, C8, C11, C14, etc) till the last study treatment. In response to AEs of special interest, such as anaphylaxis or hypersensitivity, ADA samples closer to the event may be collected, based on the judgment of the Investigator and/or medical monitor. If isatuximab is stopped and cemiplimab treatment continues, cemiplimab ADA samples should be collected as planned per PK/PD flow-chart
- ^b Isatuximab PK and ADA samples to be collected each cycle till the last study treatment. However, collection can be stopped earlier based on the updated knowledge of isatuximab PK and immunogenicity. After FUP 90(±7) days after last IMP administration, no further ADA will be sampled even if the status is positive or inconclusive.
- ^c Isatuximab predose sample (SOI) may be collected at the same time as the predose sample of cemiplimab (SOI) before cemiplimab infusion start
- ^d Follow-up procedures after the extended safety period of 90 days after last study treatment dose will not be performed anymore for patients still under treatment at the time of amended protocol 05.

Abbreviations: AB=Antibody, ADA= Anti-drug antibody, C= Cycle, D= Day, EOI= End of infusion, EOT= End of Treatment (Post-treatment Safety), FUP= Follow-up period (Post-treatment safety), ID= Identifiant, IMP=investigational medicinal product, IV= Intravenous, P=Plasma, PK= Pharmacokinetic, RNT= relative nominal time, S= Serum, SOI= start of infusion

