8.9.3 Contraceptive measures and pregnancy counseling

Females of child bearing potential or male subjects with female partners of childbearing potential shall be required to use effective contraceptive methods (double barrier method, intrauterine device, oral contraception or abstinence) prior to first study treatment, while on therapy and for 5 months following the last dose of Isatuximab and 6 months following the last dose of cemiplimab.

A woman is considered of childbearing potential (WOCBP), ie, fertile, following menarche and until becoming post- menopausal unless permanently sterile.

The following highly effective methods of contraception are accepted:

- Sexual abstinence,
- Diaphragm and spermicide PLUS male condom, or,
- Intrauterine device PLUS male condom, or,
- Medical method (such as hormonal contraceptive) PLUS male condom.

The choice of effective method is left to Investigator judgment, in accordance to local regulation. Sterilized or infertile subjects are exempt from the requirement to use of contraception. In order to be considered sterilized or infertile, subjects must have undergone surgical sterilization (vasectomy/bilateral tubectomy, hysterectomy, bilateral ovariectomy) or be a postmenopausal woman defined as 12 months or more with no menses prior to enrollment and 50 years of age.

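### Flowchart footnote c ties the AABB-bulletin and card instructions to study treatment, although Appendix I describes serologic interference for up to six months after anti-CD38 stops

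*Protocol*

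**What the plan says.** Two footnotes to the Section 1.1 flowchart deal with isatuximab's interference in blood-bank testing.

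Footnote c gives three instructions:
- Notice: "The transfusion service should be made aware that the patient is receiving an anti-CD38 treatment (isatuximab").
- Bulletin, in part: "During the study treatment period the transfusion service should follow the recommendations issued in the AABB bulletin in case a blood red cells transfusion". The same footnote says that the bulletin's web link will be printed on the study patient card.
- Cards: "Patients should keep together their study patient card with their blood type card throughout the duration of the study treatment".

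Footnote r covers the same ground with no end date:
- Cards: "Blood type card will be kept by the patient with the study card".
- Notice: "The blood bank needs to be informed that the patient is receiving a treatment with an anti-CD38".
- Testing: "On Cycle 2 Day 1 and before each transfusion: Indirect Antiglobuline Test (IAT, indirect Coombs test or Antibody screen").

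Appendix I reproduces the AABB bulletin, and Section 17 makes the appendices part of the protocol. The bulletin gives up to six months after stopping an anti-CD38 antibody as the time over which indirect antiglobulin tests (IATs) may remain positive. Its advice for patients who have started such an antibody has no end date.

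The procedure lists for end of treatment (12.4.3), follow-up (12.4.4.1 and 12.4.4.2) and the period after the final cut-off (12.4.5) do not mention the bulletin, the IAT, transfusion precautions or either card.

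**The concern.** The only sentence in the body of the protocol that directs the transfusion service to the bulletin carries a time limit that the bulletin does not have. The limit ends before the interference the bulletin describes may have ended. The card that carries the bulletin link falls under the same limit.

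Transfusion is foreseen, since footnote r requires an IAT before each one. The case at risk is a patient who has stopped treatment, no longer carries the cards, and is transfused by a blood bank unaware of the recent anti-CD38 exposure. That blood bank would see a panreactive screen. Appendix I names two consequences: delay in issuing red cells and, in some cases, a clinically significant alloantibody hidden by the interference. The same appendix bounds the harm: ABO/RhD typing and immediate-spin crossmatches are unaffected, and severe hemolysis has not been seen.

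**Working it through.** There is no sample size, power or error rate to reproduce. The check is a comparison of texts followed by calendar arithmetic.

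**Step 1. The periods side by side.**

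| Item | Source | Stated end |
|---|---|---|
| Follow the bulletin | Footnote c | Study treatment |
| Keep the two cards together | Footnote c | Study treatment |
| Keep the two cards together | Footnote r | None |
| Tell the transfusion service or blood bank | Footnotes c and r | None |
| IAT before each transfusion | Footnote r | None |
| Bulletin's advice once anti-CD38 has started | Appendix I | None |
| Possible positive IAT | Appendix I | Up to six months after stopping |

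Only the first two rows stop with treatment. Both are shorter than the last row.

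**Step 2. Length of the uncovered interval.** Six months is taken as 26 weeks: 26 × 7 = 182 days. The protocol does not define *study treatment period* for this purpose, so two readings are shown.
- It ends at the last dose: 182 − 0 = 182 days.
- It ends 30 days later, as the treatment-emergent and on-treatment periods do (Protocol 13.4.5.2, SAP 2.1.4; an assumption here): 182 − 30 = 152 days.

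Both figures assume that isatuximab is the last drug stopped. Sections 6.5.1 and 11.1.1 let one drug continue after the other is discontinued, and the patient then remains on study treatment. If cemiplimab continues alone, footnote c still applies and the interval after isatuximab shrinks.

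**Step 3. How much of the six months falls after the last planned visit.**
- The Section 1.2.2 footnote, repeated in Sections 1.2.3, 1.3.2 and 1.3.3 for patients still on treatment at amended protocol 05, reads: "Follow-up procedures after the extended safety period of 90 days after last study treatment dose will not be performed anymore". Procedures therefore run to day 90, which leaves 182 − 90 = 92 days.
- If the 30-day visit of Sections 6.6.1 and 11.1.2 is the last one, 182 − 30 = 152 days remain.

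**Step 4. After the change.** With footnote c extended to six months after the last isatuximab dose, the interval in Step 2 is 182 − 182 = 0 days.

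**What cannot be computed.** The documents give no isatuximab-specific duration of interference. The flowchart schedules the interference test only at screening and Cycle 2, and SAP 2.4.5.7 summarizes IAT results for the on-treatment period only. The documents give no transfusion rate after treatment, and no count of patients still on treatment or within six months of their last dose. The number who could benefit is therefore unknown.

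**The case against.** The strongest reply is that footnote c says what to do during treatment and does not tell anyone to stop afterwards. The bulletin is part of the protocol and states the six months itself. A service already notified, holding the baseline phenotype and the Cycle 2 Day 1 IAT from the local laboratory (footnote r, Sections 12.2 and 12.4.2), does not lose that record at the last dose. Footnote r still requires an IAT before each transfusion, and a patient who still has the study card can lead any blood bank to the bulletin. The six months is also an upper limit for the drug class, from a 2016 bulletin whose cited sources concern daratumumab. The study card text is not in the documents and may already cover the period.

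Most of this stands, and it makes the remaining risk small. It does not remove the mismatch: where the protocol states a period, that period is too short by its own appendix, and one of the two instructions concerns the card on which the reply relies.

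Three stronger readings are tempting and are not supported:
- *Footnotes c and r contradict each other.* They do not. One card instruction is bounded and the other open-ended, so a patient can follow both. They differ only in duration.
- *For patients under Section 12.4.5 the whole 182 days falls after the last planned visit.* That section limits the information collected after treatment; it does not cancel visits. Sections 6.6.1 and 11.1.2 keep a 30-day visit, and the PK/PD flowchart notes keep procedures to day 90.
- *The present tense in the two notices shows that they lapse.* Neither notice has an end date, and a service told when treatment starts keeps that information.

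**Conclusion.** The point holds as a minor wording defect in patient safety. Footnote c bounds the bulletin instruction and the card instruction by study treatment, while Appendix I describes interference for up to six months after stopping, and no later section closes the difference.

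The uncovered interval is at most about 152 to 182 days after the last isatuximab dose. About 92 days of the six months lie beyond the day-90 visit, or about 152 days if the 30-day visit is the last. These are calendar lengths, not measures of harm. They rest on six months taken as 182 days, on the class-level maximum applying to isatuximab, and on isatuximab being the last drug stopped. Counting six months as 183 days moves the figures by one day.

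A reader might infer that patients leave treatment with no transfusion safeguard. The documents do not support that, because the notices, the pre-transfusion IAT, the card link and the bulletin's own advice have no stated end. The protocol does extend another precaution past dosing, with contraception "while on therapy and for 5 months following the last dose of Isatuximab and 6 months following the last dose of cemiplimab". That shows only that a post-dose period can be written in; it is not evidence about serologic interference.

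Sample size, power, type I error and the primary analysis are untouched.

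**What to change.** 1. In footnote c, replace both time limits with: *during study treatment and for 6 months after the last isatuximab dose*.
2. State the same card period in footnote r, so that the two footnotes agree.
3. Check the study patient card and align it if it carries the treatment-only limit.
4. Add one line to Section 12.4.3: at the end-of-treatment visit, remind the patient to keep both cards for that period and show them before any transfusion. Put a cross-reference in Section 12.4.5 so that the reminder also reaches patients treated beyond the final cut-off.

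The cost is wording in two footnotes, one line, one cross-reference and possibly the card text. No visit, test or staff is added, and the change can go with the next amendment. It can help only patients still on treatment, or within six months of their last isatuximab dose, when it takes effect.
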